6.1.2.5. Day 32 (3 days \pm 1 day after second dose)

- Optional on-site visit for collection of blood sample (PBMC and plasma) for innate transcriptome gene expression – select sites only
- If subject does not attend on-site visit, scripted phone call with site to report symptoms (if unable to reach subject then email or SMS is acceptable)
- Record concomitant therapy/AEs/SAEs

6.1.2.6. Day 36 (7 days -1/+7 day after second dose)

- Perform limited physical examination
- Vital signs (blood pressure, heart rate, and temperature)
- Collect blood for serum chemistry and hematology
- Urinalysis (dipstick)
- Symptom Memory Aid reviewed
- Nasal swab into buffer for mucosal IgA and virus shedding
- Collect blood sample for humoral immunogenicity assays (MNT and other serum assays)
- Collect blood sample (PBMC) for cellular immunogenicity assays (ELISpot) – only by select sites
- Collect blood sample (plasma) for cytokine expression – only if PBMC collected by site
- Record concomitant therapy/AEs/SAEs

6.1.2.7. Day 57 (28 days \pm 7 days after second dose)

- Perform limited physical examination
- Vital signs (blood pressure, heart rate, and temperature)
- Nasal swab into buffer for mucosal IgA and virus shedding
- Collect blood sample for humoral immunogenicity assays (MNT and other serum assays)
- Collect blood sample (PBMC) for cellular immunogenicity assays (ELISpot) – only by select sites
- Record concomitant therapy/AEs/SAEs

6.1.2.8. Day 209 (180 days \pm 14 days after second dose)- on-site visit

- Perform limited physical examination
- Vital signs (blood pressure, heart rate, and temperature)
- Nasal swab into buffer for mucosal IgA and virus shedding
- Collect blood sample for humoral immunogenicity assays (MNT and other serum assays)
- Record SAEs

Due to the COVID-19 pandemic, local governments may issue stay-at-home orders which prevent centers from conducting on-site Day 209 visits. This protocol allows for the Day 209 visit to be a follow-up phone call focusing on the following safety points:

- Has the subject received any licensed vaccines since Day 1 of the trial?
- Has the subject received any investigational product (other than study IMP/placebo) since Day 1?
- Has the subject had any SAEs or medically attended AEs since the last contact with the site?

6.1.3. Testing for Influenza

During the treatment period (Day 1 – Day 57), when increased influenza infections are being reported in the geographic region of the investigational site, subjects will be asked to notify the site immediately if they experience symptoms of influenza (fever, chills, sore throat, rhinorrhea, cough, muscle/body aches). If influenza is suspected the subject will be asked to return to the site and will have nasal swabs collected for laboratory confirmation of influenza. Subjects will be reminded at every scheduled visit and phone call, and in addition to visits and calls scheduled above, will be contacted at Days 15±2, 21±2, 43±2, and 50±2 by phone or messaging. Subjects may also have a rapid diagnostic test performed and may be treated for influenza at the investigator's discretion.

6.1.4. Early Termination Visit

Subjects who withdraw consent will be asked to attend the clinic for safety evaluation as described in Early Termination assessments.

Early Termination assessments should be completed within 7 (± 3) days of discontinuation for subjects who discontinue from the study. The following assessments are to be performed:

- Complete physical examination (neurological, rectal and gynecological exams do not need to be performed unless clinically indicated); a limited physical exam will be completed if early termination occurs within 28 days after dose administration
- Vital signs (height, weight, blood pressure, heart rate, and temperature)
- Collect blood for serum chemistry and hematology
- Urinalysis (dipstick)
- Symptom Memory Aid
- Nasal swab into buffer for mucosal IgA and virus shedding
- Collect blood sample for humoral immunogenicity assays (MNT and other serum assays)
- Collect blood sample for cellular immunogenicity assays (PBMC, ELISpot) – only for select sites
- Collect blood for gene expression (PBMC, plasma) – only for select sites
- Record concomitant therapy/AEs/SAEs

6.1.5. **Unscheduled Visits**

Unscheduled visits can be planned:

- To obtain additional information to ensure safety to the subject. Additional blood and urine samples may be taken at the discretion of the Investigator.
- To obtain a nasal swab for assessment of potential influenza infection.
- To assess, confirm, and follow-up on out-of-range clinical laboratory test, or vital sign values that will determine a subject’s eligibility, or in case of a positive drug screen.
- The result of the retest will be considered for subject eligibility.

Findings made during unscheduled visits should be reported in the eCRF.

6.2. **Study Assessments**

6.2.1. **Clinical Evaluations**

6.2.1.1. **Medical History**

A complete medical history will include a review of all major body systems. Significant past and present medical history will be obtained by interview during the screening visit.

6.2.1.2. **Concomitant Medications**

Details of prescription and over-the-counter medications (including vitamins) currently used will be recorded during the screening visit. Concomitant medications will be reviewed at each visit and any new medications will be documented on the eCRF.

6.2.1.3. **Demographics**

Demographics will be obtained during screening only. Demographics will include the age and race as described by the subject.

6.2.1.4. **Physical Examination**

6.2.1.4.1. **Complete Physical Examination**

A complete physical examination will be performed for each subject at the time points specified in the Schedule of Events ([Table 3](#)). The examination will consist of assessment of the following organs/systems:

- Head
- Eyes
- Ears, nose, throat
- Neck
- Cardiovascular
- Chest

- Respiratory
- Abdomen
- Genitourinary – only if clinically indicated
- Extremities
- Musculoskeletal
- Nervous system – only if clinically indicated
- Dermatological
- Other conditions of note

6.2.1.4.2. Limited Physical Examination

A limited physical exam will be performed for each subject at the time points specified in the Schedule of Events ([Table 3](#)). The examination will include the nares (including edema), throat, and lungs (including evaluation for wheezing). A targeted physical examination may be performed on other body systems if indicated based on review of interim medical history or subject symptoms as observed by site or by PI.

6.2.1.5. Vital Signs

Vital signs include height, weight, oral temperature (°C), blood pressure (mmHg), pulse rate (beats per minute). Vital signs will be obtained at the time points specified in the Schedule of Events ([Table 3](#)). Subjects should have weight and height measured while wearing light street clothing and with shoes off. Blood pressure will be measured from the subject's arm after the subject has been seated or semi-recumbent for approximately 5 minutes with the arm supported at the level of the heart. Blood pressure will be recorded to the nearest mmHg.

6.2.1.6. Symptom Memory Aids

Subjects will be asked to record post-treatment symptoms in a Symptom Memory Aid ([Appendix 5](#)) at the time points specified in the Schedule of Events ([Table 3](#)) for reactogenicity. At time of first dose, the first entries will be in concert with study staff as a training session at pre-dose, the second entry will be the evening of vaccination and subsequent 6 entries will be made each evening following the IP delivery. Since visit Day 36 may occur ± 1 day, the subject may not complete all days listed on the memory aid prior to the first post-dose visit. For subjects who attend the clinic at Day 35, a stamped and pre-addressed envelope will be provided so that the diary may be completed and mailed to the Site. Symptoms recorded on diaries returned by mail will be reviewed with the subject by telephone, if needed. Subject diaries will be retained as source documents.

Events that are reported in the Symptom Memory Aid will be reviewed by the study staff and assessed and recorded as AEs according to the appropriate toxicity scale ([Appendix 1](#) for vital signs and systemic AEs and [Appendix 3](#) for reactogenicity assessments). During this time, subjects are asked to take their oral temperature (at approximately the same time each evening using the thermometer provided to them by the site) and record it in the Symptom Memory Aid. Any medications taken by the subjects will also be recorded in the Symptom Memory Aid. In addition,

subjects will be asked to record symptoms they may be experiencing during this time period, including:

- Feverish
- Nasal irritation
- Nasal bleeding
- Runny nose
- Stuffy nose/Congestion
- Sore/scratchy/itchy or painful throat
- Body/muscle aches
- Joint pain
- Headache
- Cough
- Body rash
- Tiredness
- Nausea
- Vomiting
- Other symptoms

6.2.1.7. Urine Samples

Urine samples for the determination of pregnancy for women of childbearing potential, drug screening, and urinalysis will be collected at the time points specified in the Schedule of Events ([Table 3](#)).

A midstream urine sample will be collected for urinalysis by dipstick for specific gravity, pH, glucose, protein, ketones, bilirubin, urobilinogen, nitrite, leukocyte esterase, and occult blood. If dipstick urinalysis is abnormal, microscopic examination for WBC, RBC, and epithelial cells will be performed. Crystals, casts, and bacteria will only be reported if present.

A urine drug of abuse screen will be performed.

6.2.2. Bioanalysis

Blood and urine samples for determination of the concentration of analytes specified in [Appendix 2](#) will be analyzed by a qualified vendor under the responsibility of the Sponsor, using validated analytical methods.

The Investigator must review the laboratory report, document this review, and record any change occurring during the study he considers to be clinically relevant in the AE section in the EDC system. Laboratory values outside the normal range will be flagged and their clinical relevance as

an AE will be assessed by the Investigator. Laboratory values which are Grade 3 or higher based on the grading scales in [Appendix 2](#) will be reported to the Sponsor **within 24 hours** of investigator awareness, and assessment of clinical relevance will be reviewed by the Medical Monitor.

The laboratory analysis will be carried out following the principles of Good Laboratory Practice (GLP) regulations.

6.2.3. Adverse Events

Adverse events will be monitored continuously from first administration of IP treatment until study Day 57. At regular intervals during the study, subjects will be asked non-leading questions to determine the occurrence of any AEs. All AEs reported spontaneously during the course of the study will be recorded as well. Solicited and unsolicited signs and symptoms will be reported as AEs after review by the Investigator or designee, either separately using the corresponding Medical Dictionary for Regulatory Activities (MedDRA) terminology of the sign or symptom or combined using the appropriate term. For example, a subject who experiences dysuria with blood, WBCs, and bacteria in the urine would be recorded as having a urinary tract infection.

For detailed definitions and reporting procedures of AEs, see [Section 9](#).

6.2.4. Efficacy Evaluations

6.2.4.1. Nasal Swabs

Nasal swabs will be collected from subjects for the following purposes:

1. To determine mucosal immunity
2. To test for the presence of shedding influenza virus
3. To test for the presence of respiratory viruses and bacteria (Optional)

Nasal swabs will be collected at the time points specified in the Schedule of Events ([Table 3](#)) from all subjects. Individual swabs will be collected from each nostril and combined into a single vial of media. Samples will be aliquoted to use in various tests.

To evaluate mucosal immunity, an ELISA-based test will be used to measure 1) mucosal IgA antibody titer to HA and 2) total IgA concentration

To detect shedding influenza virus, a quantitative H3N2 RT-PCR assay will be used. Only swabs that have a positive qRT-PCR test result will be subjected to quantitative infectious culture assay.

Possible infection with respiratory viruses and bacteria may be evaluated by use of a qualitative PCR test. This multiplexed assay will be performed by use of a commercial, qualitative viral and bacterial upper respiratory tract infection panel PCR device (adventitious agent screening).

If a subject presents within 7 days of vaccination with symptoms of fever, upper respiratory illness, nephritis/cystitis, conjunctivitis or diarrhea, regardless of the severity of the symptoms, an additional nasal swab(s) should be collected and/or analyzed outside of the defined time points.

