2.2.2. Secondary Endpoints

The secondary endpoints are:

1. The number and percentage of study participants who after one or two doses of Bris10 M2SR or placebo demonstrate:
 - i. Influenza-specific serum antibody responses measured at specified time points;
 - ii. Influenza-specific mucosal immunoglobulin A (IgA) antibody responses measured at specified time points;
 - iii. Influenza-specific cellular immune responses measured by cytokine enzyme-linked immunospot (ELISPOT) at specified time points.
2. The number and percentage of study participants who after one or two doses of Sing2016 M2SR or placebo demonstrate:
 - i. Influenza-specific serum antibody responses measured at specified time points;
 - ii. Influenza-specific mucosal IgA antibody responses measured at specified time points;
 - iii. Influenza-specific cellular immune responses measured by ELISPOT at specified sampling time points.
3. Vaccine virus shedding evaluated by influenza A-specific qPCR on day 7 post IP administration.

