24. Females who are pregnant or lactating (i.e., a nursing mother).
25. Acute febrile illness within 72 hours prior to vaccination, defined as the presence of a moderate or severe illness with or without fever (as determined by the Investigator through medical history and physical examination), or presence of a fever $>38^{\circ}\text{C}$ orally. Vaccination (or administration of the second dose of vaccine) should be delayed until the subject has recovered. Persons with a minor illness, such as diarrhea, or mild upper respiratory tract infection with or without low-grade fever, may be enrolled after resolution of the illness.
26. Any condition, in the opinion of the Investigator, (such as subjects who have medically high-risk conditions) that might interfere with the primary study objectives for safety of the study subject.
27. Previous exposure to M2SR investigational vaccine.
28. Any active military personnel/member.

Exclusions at Day 29:

Pregnancy, receipt of a prohibited medication, or new prohibited diagnosis, including laboratory confirmed influenza and/or treatment for influenza, or high-risk condition are exclusions for second vaccination.

Note: At the discretion of the investigator, subjects may be rescreened; out-of-range clinical laboratory tests may be repeated twice, and vital signs may be repeated three times. Results of any retest must be available prior to enrollment.

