8.2.1. Secretory IgA Immune Response and Viral Shedding from Nasal Swab

Summary statistics for secretory IgA immune response (influenza A-specific and total IgA ELISA) at Days 1 (baseline), 29, and 57 post IP administration will be provided.

Summary statistics for viral shedding (influenza A-specific q-PCR) at Screening, Days 1 and 8, will be provided.

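### Vaccine shedding is read with a PCR that, as described, does not separate the H3N2 vaccine viruses from circulating H3N2, and no rule classifies a positive swab

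*Protocol*

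**What the plan says.** **Endpoint.** Protocol 2.2.2 lists as the third secondary endpoint: "Vaccine virus shedding evaluated by influenza A-specific qPCR on day 7 post IP administration".

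**Assay.** Protocol 6.2.4.1 describes it with a different target: "To detect shedding influenza virus, a quantitative H3N2 RT-PCR assay will be used". It adds a second step: "Only swabs that have a positive qRT-PCR test result will be subjected to quantitative infectious culture assay". It names no gene target and no culture cell line, and does not say how a culture result changes the reading of the PCR.

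**Analysis.** SAP 8.2.1 states: "Summary statistics for viral shedding (influenza A-specific q-PCR) at Screening, Days 1 and 8, will be provided". It has no attribution step. Protocol 3.2 collects shedding swabs on Days 1, 8, 29 and 36. Table 3 marks the Screening swab for IgA only, not for virus detection.

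**Vaccines.** Protocol 1.2.4 and 1.2.5 describe both products as H3N2 viruses on a PR8 backbone that do not express M2. Protocol 5.1 says they are grown in an M2-complementing cell line.

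**Testing for natural influenza.** Protocol 6.1.3 says subjects with suspected influenza between Day 1 and Day 57 "will have nasal swabs collected for laboratory confirmation of influenza". It names no assay and also allows a rapid test. For respiratory and certain other symptoms within 7 days of dosing, Protocol 6.2.4.1 says "an additional nasal swab(s) should be collected and/or analyzed outside of the defined time points". Under the Day 29 exclusions in Protocol 4.2, a new prohibited diagnosis, "including laboratory confirmed influenza and/or treatment for influenza, or high-risk condition are exclusions for second vaccination".

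**The concern.** A shedding endpoint should answer whether the virus found in the nose is the vaccine. Here the vaccine and a seasonal virus share the subtype that the assay is said to detect. Under the label influenza A-specific, other circulating influenza A viruses could also read positive. A subject who caught influenza in the week after dosing would, on the plan's wording, be counted as shedding vaccine virus.

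The stakes are moderate. The product is described as producing no progeny after one round of infection, so even one or two apparent shedders would attract attention in a descriptive table. Without a classification rule fixed in advance, any explanation of those positives would come after the result was known.

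**Working it through.** The plan gives no figure for this endpoint, so there is nothing to reproduce. The first check sets the passages against the question; the second gives scale.

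**1. Does any stated step classify a positive swab from an individual subject?**

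- *PCR:* described as influenza A-specific or H3N2. Neither description excludes wild-type H3N2.
- *Culture:* relevant in principle, because the vaccine needs M2-complementing cells and wild-type virus does not. The cells are not named, a negative culture does not type the RNA, and both the endpoint and SAP 8.2.1 rest on PCR.
- *Day 1 pre-dose swab:* a positive there cannot be vaccine virus. It does not reveal an infection acquired between Day 1 and Day 8.
- *Placebo arm:* shows background positivity for the group, not the origin of a given positive.

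None of these is written as a rule for classifying a subject.

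**2. Scale**

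Inputs: about 40 subjects per group (SAP 12) and four active groups (Protocol Table 1), so 4 × 40 = 160 active and 40 placebo. SAP 8.2.1 summarises one post-dose time point, Day 8. The proportion p of Day 8 swabs carrying wild-type H3N2 is assumed to be 0.5% to 2% and equal across arms; the documents give no value.

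Expected false positives in the active arms = 160p. Chance of at least one = 1 − (1 − p)^160. Chance that placebo shows none = (1 − p)^40. With independence, the product of the last two is the chance of wild-type positives appearing in active arms only.

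| p | Expected, active | At least one, active | None, placebo | Active only |
|---|---|---|---|---|
| 0.5% | 160 × 0.005 = 0.8 | 55% | 82% | 0.552 × 0.818 = 45% |
| 1% | 160 × 0.01 = 1.6 | 80% | 67% | 0.800 × 0.669 = 53% |
| 2% | 160 × 0.02 = 3.2 | 96% | 45% | 0.961 × 0.446 = 43% |

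The placebo arm is therefore a weak guide. With 0 of 40 positive, the exact two-sided 95% upper limit for the background rate is 1 − 0.025^(1/40) = 8.8%.

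If the swab after the second dose (Day 36) were analysed too, and all subjects gave it, the expected counts would double to 1.6 to 6.4. The SAP as written does not include that swab.

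**The case against.** The best counter-arguments are these.

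- *There are safeguards.* Culture of PCR-positive swabs, pre-dose swabs and a randomized placebo arm all bear on the question. This stands in part. It rules out saying that nothing separates the two viruses, or that shedding cannot be assessed in season. It does not supply a rule for an individual swab.
- *The assay may already discriminate.* The Laboratory Manual is not among the documents and may name vaccine-specific targets. This stands. If it does, the fix reduces to citing those targets and adding the counting rule.
- *Exposure was limited.* Enrollment was halted because of seasonal flu, and the endpoint is descriptive. Both points stand; they favour a low assumed rate and a modest weight.

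A reader might also infer that the protocol reads the same PCR as natural influenza elsewhere, so that vaccine RNA would wrongly bar subjects from dose 2. The documents do not support that. Protocol 4.2 and 6.1.3 speak of laboratory confirmation without naming an assay. The optional panel is the only PCR tied to infection ("Possible infection with respiratory viruses and bacteria may be evaluated by use of a qualitative PCR test"), and its targets are not listed. The early symptom swab is not linked to the Day 29 exclusion. Nor do the documents say that a wild-type virus grown in culture would be recorded as infectious vaccine virus.

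**Conclusion.** The point holds for the shedding endpoint. As described, the PCR does not separate vaccine H3N2 from circulating H3N2, and no prespecified rule classifies a positive. Under the assumed 0.5% to 2% carriage, about 0.8 to 3.2 false positives would be expected among about 160 active subjects on Day 8. An active-only pattern would arise by chance in roughly 43% to 53% of such trials. These figures rest on the assumed rate, equal carriage across arms, independence, a Day 8 swab from every subject, and an assay that detects wild-type H3N2.

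The Day 29 question is narrower: the documents do not say how a positive that may reflect the vaccine itself is treated. A reader might infer biased safety results from this. That goes too far. SAP 9 analyses adverse events on the Safety Set, which keeps subjects who received one dose. SAP 8.2 assigns no analysis set to immunogenicity, and Protocol 8.1 uses the Full Analysis Set. Only the memory-aid tables (SAP 9.2.1) and the repeat exposure tables (SAP 9.1) use the Evaluable Set, which drops subjects without dose 2.

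**What to change.** **Shedding (Protocol 6.2.4.1 and SAP 8.2.1)**

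1. Type every PCR-positive shedding swab with a target that differs between vaccine and wild-type virus, such as the M2 region or the PR8 internal genes. Alternatively, read the planned culture in both M2-complementing and ordinary cells. Typing by PCR suits the endpoint better, because a swab negative in both cultures stays unclassified.
2. Count only vaccine-typed positives as shedding.
3. Tabulate wild-type, untyped and pre-dose positives separately by arm.
4. Use one assay name throughout (influenza A-specific in Protocol 2.2.2 and SAP 8.2.1; H3N2 in Protocol 6.2.4.1).
5. Reconcile the shedding days: Days 1, 8, 29 and 36 in Protocol 3.2; Screening, Days 1 and 8 in SAP 8.2.1, although Table 3 does not mark the Screening swab for virus detection.

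The cost is one extra assay on a few stored swabs, some lines of text and a short delay in classification. SAP 12 says the shedding data were not available at lock and may be analysed later, so the rule can still be set before that analysis.

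**Influenza testing**

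Protocol 4.2 (Day 29 exclusions), 6.1.3 and 6.2.4.1 should be reconciled. They should name the confirmation assay and state how a positive that may reflect the vaccine is treated. No clinical rule is proposed here.
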